The scientific goals of this proposal are to further characterize tinnitus and PTSD symptomatically (Aim 1), neurobiologically characterize tinnitus and PTSD, independently and conjointly (Aim 2), and apply modeling to psychometric and neurofunctional data (Aim 3). We will recruit veterans and active duty service members with tinnitus and PTSD, PTSD only, tinnitus only, and healthy controls. We will assess participants for PTSD, tinnitus, hearing loss and other audiologic disorders, and conduct resting-state functional magnetic resonance imaging (rs-fMRI).

Specific Aim 1: To further characterize the cognitive, behavioral, and emotional symptoms associated with both
 tinnitus-related distress and PTSD.

Hypothesis 1: Canonical correlations will identify both shared and unique symptoms between tinnitus-related distress and PTSD.

Specific Aim 2: To identify the functional connectivity patterns in the auditory-vigilance network associated with both tinnitus and PTSD.

- Hypothesis 2a: Dysregulated connectivity within the auditory-vigilance resting state network will be implicated among
 individuals with both tinnitus and PTSD.
- 46
 47 Hypothesis 2b: Individuals with tinnitus and PTSD will demonstrate unique patterns of dysregulation within the 48 auditory-vigilance network versus those with only PTSD, only tinnitus, and healthy controls.

50 Specific Aim 3: To identify specific regions within the auditory-vigilance network that correspond with tinnitus-51 related distress and PTSD symptom severity.

53 Hypothesis 3: Dysregulated activity within regions of the auditory-vigilance network will be correlated with symptom

clusters of both tinnitus-related distress and PTSD. HUMAN SUBJECTS RESEARCH PROTOCOL

Page **3** of **20**

56 4. BACKGROUND AND SIGNIFICANCE.

57 Tinnitus and PTSD at the Symptom/Impairment Level

At the symptom and impairment levels, research supports the notion of shared mechanisms between tinnitus and PTSD,
 including (1) overlapping symptoms between tinnitus-related distress and PTSD; (2) comorbidity between tinnitus and
 PTSD; and (3) functional outcomes of individuals with both disorders.

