6.2. Study Procedures and Description of Assessments

A trained research staff member will explain the study to potential participants in a private location and give them a copy of the informed consent document to read. The staff member will review the risks and benefits of the study and ensure the potential subject understands the research. Once consent is given, the screening assessments will then be scheduled. Timing of assessments will be determined by participants' availability. Group assignment, main outcomes, and participant characterization measures are described below. **Table 1** lists assessments.

259 Group Assignment

Participants will be assigned to one of four groups, based on results of audiometric assessments and the Clinician 260 Administered PTSD Scale for DSM-5 (CAPS-5), explained below. Those who indicate they have bothersome tinnitus and 261 262 meet criteria for PTSD on the CAPS-5 (conducted by an independent evaluator), will be assigned the Tinnitus and PTSD Group (T&P). Those who do not endorse tinnitus and meet criteria for PTSD will be assigned to the PTSD Only Group 263 264 (PO). Those who indicate they have bothersome tinnitus but do not meet criteria for PTSD will be assigned to the Tinnitus Only Group (TO). Those who do not endorse tinnitus and do not meet PTSD criteria on the CAPS-5 will be assigned to 265 266 the Healthy Control Group (HC). All will then be scheduled for an fMRI scan. Participants will be matched across groups for sex, age, head injury, length of military service, number of deployments, and hearing loss. Measures used for group 267 268 assignment and characterization are explained below.

270 Assessment Instruments.

The audiometric assessments will be conducted at the Hearing Center of Excellence (60 minutes). Repeat tinnitus acoustic assessment only (see description below) may be completed at the RII prior to the fMRI for eligible participants with tinnitus when an evaluator is available (30 minutes).

Self-report instruments may be administered at the Hearing Center of Excellence, at the STRONG STAR offices, or via
 online data capture, Clinical interviews may be administered at the STRONG STAR offices or via phone or video
 conferencing. These assessments are estimated to take approximately 90 minutes.

278

282

284

269

274

258

fMRI scans will be conducted at the Research Imaging Institute (60-75 minutes). Participants will be asked whether they

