507 Analysis Plan: Non-inferential statistics will be calculated to include central tendencies, standard deviations, and alpha coefficients. Prior to analyzing data, unusual distributions, missing data, or outliers will be identified. Descriptive 508 509 statistics will be used to summarize participant characteristics. Group differences will be tested using t-tests, Chi-Square, or Fisher's exact tests as needed. Canonical correlations will be conducted on the data of all 60 participants from the T&P 510 and TO groups, using the subscale scores of the CAPS-5 and the TFI. Canonical correlations identify and measure 511 512 associations among two sets of variables and will identify latent variables between tinnitus-related distress and PTSD 513 symptoms. The 12 total subscales from the CAPS-5 and TFI will be entered into the analyses, requiring 60 participants for 514 large effect sizes (Steven, 1986).

515

516 Hypothesis 2a: Dysregulated connectivity within the auditory-vigilance resting state network will be implicated among

517 individuals with both tinnitus and PTSD.

- 518 Hypothesis 2b: Individuals with tinnitus and PTSD will demonstrate unique patterns of dysregulation within the auditory-
- 519 vigilance network, versus those with only PTSD, only tinnitus, and healthy controls.

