Analysis plan: rs-fMRI provides valuable information about neurobiological mechanisms that influence 520 neurological and psychiatric conditions at rest (Menon, 2011). To test our conceptual model and deduce neurobiological 521 mechanisms, we will use an existing, well-documented, 20-component parcellation scheme of the resting-state networks 522 (Laird et al., 2011; Auditory Component 16). After extracting the A1/VAN, we will use group information-guided 523 524 independent components analysis (GIG-ICA) to determine intra-network connectivity differences between those with both 525 tinnitus and PTSD, only PTSD, only tinnitus, and healthy controls. Our team (Vanasse et al., 2019) found robust 526 differences between active-duty service members with PTSD, combat controls, and civilian control (50 active-duty with 527 PTSD, 28 combat-exposed controls, and 25 civilian controls). Based on those results, 120 participants (30 per group) in 528 this proposed study, a priori power analyses demonstrated power of 80% when $\alpha = 0.05$, to detect an effect size of d = 529 0.31 (ANOVA: Fixed effects, omnibus one-way; Faul et al., 2007). Secondary analyses will examine functional connectivity between A1/VAN and other resting-state networks. 530 531

532 Hypothesis 3: Dysregulated activity within regions of the auditory-vigilance network will be correlated with symptom 533 clusters of both tinnitus-related distress and PTSD.

534 Analysis plan: Correlations will be conducted between functional connectivity within the auditory-vigilance resting state 535 network with tinnitus-related distress and PTSD symptoms. Power analyses predict that 57 participants will achieve a 536 power of .95, with an effect size d = .45, and alpha = .05 (R Core Team, 2014).

538 Missing data. If missing data can be assumed to be missing at random, likelihood-based mixed model analysis will 539 provide valid inferences using data from all cases with any outcome data. The impact of attrition on analyses will be addressed by comparing those who are available for analysis at each assessment with those who are not using 541 appropriate data from prior assessments. 542

543 6.5 Confidentiality

537

544

554

557

563

564

568

569

570

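### The Hypothesis 3 power statement labels as d = .45 what reproduces as r = .45 for a single two-sided correlation; the number of correlations, their error control and the sample are not stated

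*Combined protocol and SAP*

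**What the plan says.** Section 6.4.2, Hypothesis 3: "Dysregulated activity within regions of the auditory-vigilance network will be correlated with symptom" clusters of tinnitus-related distress and of PTSD. The analysis plan beneath it reads "Correlations will be conducted between functional connectivity within the auditory-vigilance resting state" network and the two sets of symptoms. It then says that 57 participants will achieve a "power of .95, with an effect size d = .45, and alpha = .05", citing R. It does not say whether the test is one- or two-sided.

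Specific Aim 3 in section 3 is also plural: "To identify specific regions within the auditory-vigilance network that correspond with tinnitus"-related distress and PTSD severity.

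Hypothesis 1, in the same section, does name its sample and its variables: "Canonical correlations will be conducted on the data of all 60 participants from the T&P" and TO groups, and "The 12 total subscales from the CAPS-5 and TFI will be entered into the analyses". Hypothesis 3 has no matching sentence on who enters, which connectivity measures and scores are used, or how many correlations are tested. No multiplicity method appears anywhere in the document.

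Section 6.2 (Group Assignment) bears on who can contribute a tinnitus score: "Those who do not endorse tinnitus and meet criteria for PTSD will be assigned to the PTSD Only Group", and "Those who do not endorse tinnitus and do not meet PTSD criteria on the CAPS-5 will be assigned to" the Healthy Control Group.

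**The concern.** Cohen's d measures a difference between two means, whereas the planned analysis is a correlation. A reader who takes the label at face value will think the study can detect an effect less than half the size of the one it was sized for, and will misjudge both a null result and the design.

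The .95 describes one test at .05, but the hypothesis involves at least two correlations (one tinnitus score, one PTSD score) and probably more. With neither a listed family nor a rule for what counts as support, the error rate of the eventual claim is undefined. With no named sample, the choice of groups also stays open until results are visible.

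**Working it through.** **Inputs from section 6.4.2:** n = 57, power .95, effect .45 labelled d, alpha .05. Sidedness is not stated, so both were tried.

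**Formula.** Two-sided correlation test by Fisher z with the small-sample term:
power ≈ Φ{[atanh(r) + r/(2(n−1)) − atanh(r_c)]·√(n−3)}, where r_c = √[t²/(t² + n − 2)] and t is the two-sided critical value on n − 2 degrees of freedom.

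**Step 1. Reproduce the plan's figure with r = .45.** At n = 57, t = 2.004, r_c = .261 and atanh(r_c) = .2670. Also atanh(.45) = .4847 and .45/112 = .0040. Power = Φ[(.4847 + .0040 − .2670)·√54] = Φ(1.629) = .948. The unrounded n for .95 is 57.5. The plain Fisher formula gives .945 and the exact test .949. One-sided, r = .45 gives .972 to .983 and does not match.

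**Step 2. Read d = .45 literally.** With an equal split, r = d/√(d² + 4) = .45/√4.2025 = .2195. Then atanh(.2195) = .2231 and .2195/112 = .0020, so power at 57 = Φ[(.2231 + .0020 − .2670)·√54] = Φ(−.308) = .38. About 263 participants would be needed for .95. Conversely, r = .45 corresponds to d = 2r/√(1 − r²) = .90/.893 = 1.01.

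**Step 3. False positives if any one significant result counts.** For independent tests at .05 the chance of at least one is 1 − .95² = .098 for 2 and 1 − .95¹² = .46 for 12. Scores from one person are correlated, so null data were simulated (40,000 datasets, n = 60, one connectivity measure against m scores, correlation .3 to .7 among scores):

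| m | chance of at least one false positive |
|---|---|
| 2 | .08 to .09 |
| 12 | .24 to .40 |

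Twelve is the subscale count given for Hypothesis 1, used here as an assumption. Several regions would enlarge the family.

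**Step 4. Power if both a tinnitus and a PTSD correlation are required.** Each is tested at .05. At n = 60 single-test power is .958; if the tests were independent, joint power would be .958² = .918. With correlated scores, simulation gives about .92 to .93.

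**Step 5. Power per test under error control (r = .45, n = 60).**

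| Method | 2 tests | 12 tests |
|---|---|---|
| Bonferroni (alpha .05/m) | .93 | .79 |
| Holm, all correlations real | about .95 | about .9 |
| 5% FDR, all correlations real | about .95 | about .95 |

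**Step 6. Detectable r at 80% power, n = 60:** .35 for one test; with Bonferroni, .39 for 2 tests and .45 for 12. Holm and FDR reject at least whatever Bonferroni rejects, so the last two are conservative.

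**The case against.** **The arithmetic is sound.** It is: 57, .95 and .45 agree once .45 is read as r. Section 6.4.2 also writes d for the omnibus ANOVA of Hypothesis 2, so the letter may be a loose symbol for effect size. That explains the slip but does not remove it, because the printed figure still means something else. Nor is r = .45, two-sided, the only route near 57. A point-biserial test with r = .45 gives .962, and a one-sided test with .45 taken as a Fisher z value gives n = 57. Neither fits both the label and the two-variable correlation described, but they are a reason to ask the sponsor to confirm.

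**The word both may mean a conjunction.** If support needs a tinnitus and a PTSD correlation together, the pair needs no alpha correction. This stands, and it removes the roughly 9% figure for two tests. It does not remove inflation across several regions or symptom clusters, and the power to quote is then the joint one.

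**A reader might infer that .95 is out of reach after correction, or that 67 participants (2 tests) or 90 (12 tests) are needed.** Those counts hold for Bonferroni only. Under Holm for 2 tests, or FDR, power at n = 60 stays at about .95 if all correlations are real. The documents do not support the flat claim.

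**A reader might also infer that the analysis uses T&P alone, or that all 120 would not help the tinnitus scores.** The first conflicts with a statement sized on 57. The second needs TFI values that the documents do not give, and an assumption of no group difference in connectivity, which runs against Hypotheses 2a and 2b. Table 1 lists the TFI without restricting it to tinnitus groups, so a limit of 60 is an inference from group assignment rather than a stated rule.

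**Conclusion.** The point holds, and is worth fixing before analysis. The effect size is mislabelled. The calculation matches r = .45, two-sided, one test (power .948); a true d of .45 would have power .38 at 57 (equal split assumed). This does not show that the study is underpowered for what its authors probably intended; it shows that the intended effect is much larger than the printed one suggests.

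Separately, the statement covers one correlation, and the plan fixes neither the family nor a decision rule. The cost is a false-positive chance of about 9% (2 scores) or 24% to 40% (12 scores) if any one result suffices, or joint power of about .92 to .93 instead of .95 if both are required. These figures assume n = 60, one connectivity measure and correlations of .3 to .7 among scores; joint power also assumes that both correlations equal .45. The count of 12 is illustrative.

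**What to change.** In section 6.4.2, Hypothesis 3:

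1. Confirm that r was meant and, if so, replace d = .45 by r = .45, two-sided, one test. If d was meant, redo the calculation.
2. Before results are seen, list the connectivity measures and symptom scores that form the family and control it by Holm or 5% FDR; or state that support requires both a tinnitus and a PTSD correlation, each at .05, and how several regions or clusters are then handled.
3. Name the sample for each score. Analysing tinnitus scores in the T&P and TO participants (60) fits the stated 57 and avoids a correlation driven by people who report no tinnitus. Say which groups enter for PTSD scores.
4. Restate the sensitivity for that sample and family, for example detectable r at 80% power with n = 60: .35 for one test and, as conservative Bonferroni bounds, .39 for 2 and .45 for 12.

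The cost is a few sentences and a line of analysis code, with no extra participants or data. The stated power becomes slightly less favourable, and fewer correlations will be nominally significant.
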